1.3 Hypotheses

A high blood eosinophil count present at the time of no exacerbation is a biomarker identifying a phenotype of COPD associated with an increased rate of exacerbations at all levels of treatment in patients who are not actively smoking. High blood eosinophil counts are associated with an increased risk of short-term re-admission to hospital for COPD exacerbation.

Medical costs associated with COPD are meaningfully higher in patients with high blood eosinophil counts than in patients with normal counts.

Especially the subgroup of patients with COPD on triple therapy who have high blood eosinophil counts and are at risk of exacerbation account for high future health care resource use (HRU) and associated costs.

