Cox-proportional hazard regression with the time from hospital discharge date to the first re-admission date as the survival time, is performed to estimate HRs with 95% CI for the association between high blood eosinophil counts and time to re-admission over time periods

of 28 days, 12 weeks and 12 months, adjusted for potential confounders following the procedure as described for sub-study 1.

Table 1. Example of a life-table describing the time at hospital re-admission, by blood eosinophil count

Number of patients with high blood eosinophil count					Hazard probability	Survival probability
Weeks	At risk at start	Re-admission	Censored	Death		
4						
8						
12						
26						
36						
52						
Number of patients with normal blood eosinophil count					Hazard probability	Survival probability
Weeks	At risk at start	Re-admission	Censored	Death		
4						
8						
12						
26						
36						
52						
Total population					Hazard probability	Survival probability
Weeks	At risk at start	Re-admission	Censored	Death		
4						
8						
12						
26						
36						
52						

3.4.3 Outcome analyses sub-study 3

Means of the number of events per person year of follow up with standard deviations (SD) will be reported for count variables next to distributions (number and percentage) of categorical variables describing HRU in the baseline and outcome year. HRU events recorded at the index date are included in the baseline year, except medication prescriptions for which prescriptions at the index date are included in the outcome year.

Costs will be described as means with standard deviations. Costs of 4 subgroups of patients on Triple therapy at high risk of exacerbations will be compared with overall mean costs of patients with COPD in the total population by calculation of costs ratios with 95% confidence intervals, estimated by 1000 bootstrap replicates.

Non-parametric Mann-Whitney tests are performed to test differences in average costs between different populations of patients.

3.4.4 Outcome analyses sub-study 4

Two one or two-step generalized linear models with gamma distribution and log link will be used to perform regression analysis with total all-cause and total COPD-related costs as the outcome variables.

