Table 2 shows that 14% of patients are estimated to be on triple therapy of whom 25% is estimated to have a history of 2 or more exacerbations in the past 12 months or >1 hospitalisation. Thus, around 3.5% of patients are expected to be available for analyses on the association between high blood eosinophil counts and HRU / costs of whom 57% will not be actively smoking.

A total number of 979 patients on Triple Therapy with 2 or more exacerbations in the baseline year are required to find a 0.3 standard deviation greater amount of costs in patients with high blood eosinophil counts compared with patients with normal counts (Figure 7).

3.6.4 Sub-study 4

Figure 7 shows that a total number of 2,200 patients are required to find a difference of 0.2 standard deviations in logarithmically transformed costs between groups with and without high blood eosinophil counts with 80% power ($\alpha=0.05$), assuming a frequency of 10% for blood eosinophilia.

[figure not shown]

Figure 7. Total number of patients required (Y-axis) to find standardised differences in logarithmically transformed costs between groups with and without high blood eosinophils

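### Sub-study 3 uses Mann-Whitney tests as if they tested mean costs, and section 3.4.3 neither names nor estimates the high-versus-normal contrast the sub-study was sized on

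*Protocol*

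**What the plan says.** Section 3.4.3 describes costs by means and standard deviations. The costs of four subgroups of at-risk triple-therapy patients (high or normal count, smoking or not) "will be compared with overall mean costs of patients with COPD in the total population by calculation of costs ratios", with confidence intervals from 1000 bootstrap replicates. The only hypothesis test for costs follows: "Non-parametric Mann-Whitney tests are performed to test differences in average costs between different populations of patients". The populations to be compared by that test are not listed.

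Section 3.6.3 sizes the sub-study on another contrast. "A total number of 979 patients on Triple Therapy with 2 or more exacerbations in the baseline year are required" in order "to find a 0.3 standard deviation greater amount of costs in patients with high blood eosinophil counts compared with patients with normal counts". It introduces this group with the words "around 3.5% of patients are expected to be available for analyses on the association between high blood eosinophil counts and HRU / costs". The synopsis states the same effect on the logarithm of total costs, and the caption of Figure 7, from which the number is read, also refers to log costs.

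Objective 3B and section 2.5.3 set the total COPD population with eosinophil counts as the benchmark. They do not remove the subgroups from it.

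**The concern.** There are two separate problems.

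First, a Mann-Whitney test asks whether values in one group tend to exceed those in the other. It speaks to means only under conditions such as a pure shift between distributions of the same shape. The protocol itself treats costs as skewed: it sizes on log costs and models them with a gamma distribution and log link in sub-study 4. If high-eosinophil patients have more variable costs, for instance because a few have expensive admissions, the test can reject when mean costs are equal or stay silent when they differ. A report could then show a cost ratio and a p-value that point in different directions.

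Second, a reader of section 3.6.3 expects an estimate of high against normal counts within at-risk triple therapy. The one comparison named in section 3.4.3 sets each subgroup against all COPD patients. All four subgroups are selected on triple therapy and exacerbation history, so a ratio above 1 is expected from that selection alone and does not isolate the eosinophil count.

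**Working it through.** **Inputs.** From section 3.6.3: difference 0.3 SD; total 979; target group 3.5% of patients; 57% not smoking. From the sub-study 4 paragraph that shares Figure 7: "with 80% power ($\alpha=0.05$), assuming a frequency of 10% for blood eosinophilia". I apply that power, alpha and 10% prevalence to sub-study 3 and assume a two-sided test, since sidedness is not stated.

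**1. The plan's own figure.** For two means with a share p in one group, N = (1.960 + 0.842)² / (p(1 − p)d²) = 7.849 / (0.1 × 0.9 × 0.3²) = 7.849 / 0.0081 = 969. Rounding within groups gives 970 (873 + 97), and the noncentral t gives 971. The stated 979 is reproduced within 1%; a one-sided test would need only 764. The same formula with d = 0.2 gives 7.849 / 0.0036 = 2,180 against the stated 2,200 for sub-study 4. Sub-study 3 was therefore sized on a two-group comparison of high with normal counts, split 10/90 and pooled over smoking.

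**2. Mann-Whitney against mean costs.** The split of 979 is 98 high and 881 normal. Costs are simulated as log-normal, with log-SD 1.0 in the normal group and s in the high group. The log-SDs are assumptions, because the protocol gives none. Equal means require a log-mean difference of (1 − s²)/2, so the median ratio is exp((1 − s²)/2). Equal medians imply a mean ratio of exp((s² − 1)/2). Rejection rates at 5% are from 3,000 to 6,000 samples per cell; ranges show the spread between simulation runs.

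| s | Equal means: median ratio | Rejects | Equal medians: mean ratio | Rejects |
|---|---|---|---|---|
| 1.0 | 1.00 | 5% | 1.00 | 5% |
| 1.1 | 0.90 | 16–17% | 1.11 | 6% |
| 1.2 | 0.80 | 45–46% | 1.25 | 7% |
| 1.3 | 0.71 | 75–77% | 1.41 | 8% |
| 1.5 | 0.54 | 98% | 1.87 | 9% |

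For s of 1.1 and above, nearly all the equal-means rejections point to lower costs in the high group, although the means are the same. With equal log-SDs and a pure shift of 0.3 SD, the test is valid and has about 78 to 79% power at 979. Its relative efficiency of 3/π implies 971 × π/3 = 1,017 patients for 80%.

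**3. Where the sized contrast appears.** Section 3.6.3 sizes high against normal within at-risk triple therapy. Section 3.4.3 names subgroup against total and gives no high-versus-normal ratio. Section 3.4.4 does give adjusted relative costs for high against normal, but in the wider COPD population. It is sized separately, and its only named eosinophil interaction is with smoking.

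**4. Overlap with the total population.** The subgroup shares are 3.5% × 10% × 57% = 0.20%, 3.5% × 10% × 43% = 0.15%, 3.5% × 90% × 57% = 1.80% and 3.5% × 90% × 43% = 1.35%. A ratio R against everyone else becomes R / (share × R + 1 − share) against the total. With R = 2 this is 1.996 at a share of 0.20% and 1.965 at 1.80%.

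**The case against.** Much can be said for the plan.

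- *The sized contrast is excluded.* A reader might infer this, but the text does not say so. The Mann-Whitney sentence leaves its populations open and could cover high against normal. Dividing two of the planned subgroup ratios would also give a high-to-normal point estimate within a smoking stratum. What stands is narrower: the contrast is not named, and neither a pooled estimate nor an interval for it is planned.
- *The total-population comparator is wrong.* It is the declared objective 3B and a legitimate descriptive benchmark. The subgroups do sit inside it, but the overlap is at most about 2% and barely moves the ratio. It matters only for how the bootstrap resamples, and for independence if Mann-Whitney is run as subgroup against total.
- *The cost hypothesis goes untested.* Section 1.3 expects that "Medical costs associated with COPD are meaningfully higher in patients with high blood eosinophil counts than in patients with normal counts". That statement concerns COPD patients in general, and sub-study 4 addresses it.
- *The study is underpowered by smoking.* Splitting 979 by the 57% gives 558 and 421 patients, with about 56% and 45% power for 0.3 SD. The protocol never claims 80% within smoking strata, and 979 is a requirement, not an expected count or a cap. These figures contradict nothing stated.
- *The simulated rates rest on assumed spreads.* They do, and with equal log-SDs the problem vanishes. The protocol gives no ground for assuming equality, and the bootstrap in the same section already addresses means directly.

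**Conclusion.** The concern holds in limited form. Section 3.4.3 assigns Mann-Whitney a quantity it does not test. How far its p-values could depart from the mean-cost ratios depends on unequal spread that the protocol does not quantify: from no distortion at equal log-SDs to rejection in about three samples in four at 1.3 against 1.0, with equal means. That range assumes log-normal costs and a 98/881 split. In addition, the contrast behind the 979 is neither named nor given an effect estimate in the analysis section, and sub-study 4 does not supply it for at-risk triple-therapy patients.

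No stated number is wrong. The 979 is reproduced for the pooled contrast on log costs, the bootstrap cost ratios stand, and objectives 3A and 3B can still be answered. The documents do not support reading this as a failed sample size or an invalid benchmark.

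**What to change.** In section 3.4.3:

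1. Delete the Mann-Whitney cost tests, or describe them as tests of distributions. Base statements about mean costs on the bootstrap intervals.
2. Name the mean-cost ratio of high to normal counts within at-risk triple-therapy patients, pooled over smoking, as the contrast the sub-study was sized for. Give it a patient-level bootstrap interval or an adjusted gamma, log-link model of the kind used in sub-study 4. Report smoking strata as secondary.
3. Keep the objective 3B comparison with the total population, and resample the whole cohort in each bootstrap replicate so that the small overlap is carried through.

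In section 3.6.3, state that 979 powers only the pooled contrast and that it was computed for log costs, so the 80% does not carry over automatically to a ratio of arithmetic means.

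This costs some wording and a few more model runs. It needs no new data.

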1.4 Objectives

1. To study the association between high blood eosinophil counts at the time of stable COPD (i.e., no recent exacerbation and stable treatment during the study period) and the prospective exacerbation rate in different subgroups of patients with COPD defined by treatment regimen and smoking habits and to study whether this association is also found in patients with good adherence to ICS
2. To study whether patients admitted to hospital for COPD exacerbation are more likely to be re-admitted if their pre-admission eosinophil count (assessed at the time when there was no recent exacerbation) is high
3. A. To estimate mean all-cause and COPD-related health care resource use (HRU) and associated costs in 4 subgroups of patients who are at risk of exacerbations (i.e. a history of ≥ 2 exacerbations or ≥ 1 exacerbation leading to hospitalisation in the past 12 months) while receiving treatment with triple therapy, where the 4 subgroups are defined by the presence or absence of high blood eosinophil counts and current smoking habits
B. to compare HRU and costs with those for the total population of patients with COPD who have blood eosinophil counts available
4. To study whether the presence of high blood eosinophil counts is associated with greater all-cause and COPD-related costs in the subsequent year and to study which other easily accessible characteristics drive future costs in patients with COPD

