The risk of COPD-related re-admission to hospital for COPD within 4 weeks and 1 year will be compared for patients with and without high blood eosinophil counts year prior to index date. All analyses will be adjusted for potential confounders in multiple regression analysis.

[figure not shown]

Figure 3. Study design objective 2

2.5.3 Objective 3

The ID of objective 3 will be the most recent blood eosinophil count recorded at the time of no recent exacerbation (Figure 4).

HRU and costs, broken down by type of utilisation and total costs will be assessed in both a baseline year prior to ID and a follow-up year (outcome year) after ID.

Mean all-cause and COPD-related HRU and associated costs will be estimated in one follow-up year after the eosinophil count in the following 4 subpopulations, defined in a baseline year, of patients with COPD on triple therapy, who are at high risk of exacerbations (i.e. a history of ≥ 2 exacerbations or ≥ 1 exacerbation leading to hospitalisation in the baseline year):

Patients with high blood eosinophil counts who are:

1. not actively smoking
2. actively smoking

Patients with normal blood eosinophil counts who are:

3. not actively smoking
4. actively smoking

Mean HRU and costs will be compared with values observed in the total population of patients with COPD who have blood eosinophil counts available.

Figure 4. Study design 2

[figure not shown]

Figure 4. Study design objective 3

2.5.4 Objective 4

The ID of objective 4 will be the most recent blood eosinophil count recorded at the time of no recent exacerbation with one baseline year prior to index date for assessment of potential predictors of costs.

Total all-cause and COPD-related medical costs will be assessed in the outcome year after ID (Figure 5).

Two multiple regression analyses will be performed with total all-cause costs and total COPD-related costs as outcome variables. All potential predictors will be evaluated as independent variables, including blood eosinophil counts and its interaction with smoking status.

[figure not shown]

Figure 5. Study design objective 4

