4. BMI
5. Blood eosinophil count
6. Most recent MRC score
7. Most recent FEV₁ % predicted, with separate category for missing
8. Baseline number of exacerbations
9. Comorbidities (Diagnostic Read code prior to index date):
 - a. Asthma ever
 - b. Allergic / non-allergic rhinitis
 - a. Never
 - b. Active⁹
 - c. Ever, not active
 - c. Eczema diagnosis

⁸ For comorbidities, ‘active’ refers to those for which a diagnosis was recorded within the baseline year and/or a prior diagnosis was accompanied by a prescription for the comorbidity within the baseline year. ‘Ever’ refers to diagnosis at any time before or during the baseline period

⁹ For comorbidities, ‘active’ refers to those for which a diagnosis was recorded within the baseline year and/or a prior diagnosis was accompanied by a prescription for the comorbidity within the baseline year. ‘Ever’ refers to diagnosis at any time before or during the baseline period

- a. Never
 - b. Active
 - c. Ever, not active
 - d. Nasal polyps ever
 - e. Chronic sinusitis diagnosis ever
 - f. Gastro-oesophageal reflux disease (GERD) ever
 - g. Diabetes Mellitus ever
 - h. Osteopenia / Osteoporosis ever
 - i. Hypertension ever
 - j. Obstructive Sleep apnoea ever
 - k. Cataract ever
 - l. Ischaemic heart disease ever
 - m. Heart failure ever
 - n. Psychiatric conditions / Anxiety/ Depression ever
 - o. Sleep disorders ever
 - p. Chronic kidney disease ever
 - q. Osteoporosis (Read code diagnosis or osteoporosis drugs [bisphosphonates, denosumab, strontium ranelate or teriparatide] ever
10. Charlson comorbidity index
11. Therapy prescribed in the baseline year (yes/no)
- a. ICS / LABA
 - b. SABA
 - c. SAMA
 - d. LAMA
 - e. Theophylline

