Univariate analyses will be performed to estimate unadjusted associations for all candidate predictors of total costs (see paragraph 3.3.3 for list).

All candidate predictors will be fed into a multiple regression analysis with backwards selection of the model with the best fit, based on Akaike's information criterion (AIC). An interaction term of blood eosinophil counts and smoking status will be included in the model as potential predictor next to the main effects to evaluate relevant modification of the independent effect of blood eosinophil counts by different smoking habits.

Relative costs adjusted for other predictors will be estimated from the model for patients with and without high blood eosinophil counts.

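### Sub-study 4 lets AIC backward selection delete its own exposure, so the adjusted eosinophil cost ratio may go unreported or be reported only after passing a data-driven threshold

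*Protocol*

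**What the plan says.** Section 1.4 gives objective 4 two parts. The first is "To study whether the presence of high blood eosinophil counts is associated with greater all-cause and COPD-related costs in the subsequent year"; the second asks which other characteristics drive costs. Section 1.3 states a directional hypothesis for the first part: "Medical costs associated with COPD are meaningfully higher in patients with high blood eosinophil counts than in patients with normal counts". Section 3.6.4 sizes it as a contrast of two groups, with and without high counts.

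The analysis text treats the exposure as one candidate among many:

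- Section 3.3.3, candidate predictors of total costs, item 5: "Blood eosinophil count".
- Section 2.5.4: "All potential predictors will be evaluated as independent variables, including blood eosinophil counts and its interaction with smoking status".
- Section 3.4.4: "All candidate predictors will be fed into a multiple regression analysis with backwards selection of the model with the best fit", on AIC. The synopsis repeats the rule.
- Section 3.4.4, on the eosinophil-by-smoking interaction: it "will be included in the model as potential predictor next to the main effects".
- Section 3.4.4, on the result: "Relative costs adjusted for other predictors will be estimated from the model for patients with and without high blood eosinophil counts".

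Section 3.4.4 also provides unadjusted associations for every candidate. It does not say what adjusted figure is given if the eosinophil term is removed.

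**The concern.** Backward selection on AIC suits the second half of objective 4, where the question is which characteristics predict cost. It does not suit the first half, where the exposure is named in advance and its adjusted effect is the result. If the term is deleted, the promised adjusted comparison does not exist. If it is kept, it was kept because its estimate was far enough from zero in the same data, and a routine interval or p-value from the final model takes no account of that.

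The protocol handles the same exposure differently elsewhere. In section 3.4.1, and by reference in 3.4.2, the exposure stays in the model and covariates are judged by how far they move its coefficient. Section 3.4.4 reverses this without giving a reason. It also sits badly with section 3.5.1, which promises adjustment for all potential confounders; AIC may delete those as well.

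**Working it through.** **Inputs.** From section 3.6.4: 2,200 patients, a difference of 0.2 SD in log costs, 10% with high counts, 80% power, alpha 0.05. Two-sided testing is assumed, since the protocol does not state sidedness. The number of linked patients available to sub-study 4 is not given, so 2,200 is used, with 10,000 as an assumed larger case.

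**The plan's own figure.** N = (1.960 + 0.842)² / (0.2² × 0.10 × 0.90) = 7.85 / 0.0036, about 2,181. This is within 1% of 2,200. Power at 2,200 is 80.4% (normal approximation). A one-sided test would need 1,718 and does not match. The stated figure is thus that of a fixed two-group test, with no selection step.

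**The AIC threshold.** Removing a 1-df term lowers AIC unless its likelihood-ratio chi-square exceeds 2, so the term stays when |z| > √2 = 1.414. P(chi-square with 1 df > 2) = 0.157. The standard error at 2,200 is √(1 / (2,200 × 0.09)) = 0.071 SD, so the estimate must exceed 1.414 × 0.071 = 0.10 SD.

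**Consequences at N = 2,200** (normal approximation, lone 1-df term):

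| True effect (SD) | Kept | Mean estimate when kept | Coverage of ordinary 95% interval when kept |
|---|---|---|---|
| 0 | 15.7% | 0 (mean absolute size 0.133) | 68% |
| 0.05 | 25.6% | 0.124 (about 2.5 times the truth) | 84% |
| 0.1 | 50.0% | 0.156 (+56%) | 94.5% |
| 0.2 (planned) | 91.9% | 0.212 (+6%) | 97.3% |

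At 10,000 patients the effect of selection at 0.2 SD is negligible, but coverage among kept terms at the null is still 68%.

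**Check in the planned model family.** Gamma log-link models were simulated with 2,200 patients, eight covariates and backward AIC, 400 runs per effect. The exposure was kept in 16%, 50% and 88% of runs at true effects of 0, 0.1 and 0.2 log units. Mean estimates when kept were 0.153 at 0.1 and 0.206 at 0.2. Coverage among kept terms at the null was 58%, from only 65 fits. In the full model, with nothing removed, coverage was 93.8% to 94.0% at all three effects.

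**Type I error.** Among null terms that are kept, 0.05 / 0.157 = 32% have p < 0.05. Over all data sets the chance is 0.157 × 0.318 = 0.05, which is nominal.

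**With the interaction as a further candidate.** If main effect and interaction are dropped or kept together, null retention is 13.5% (2 df, P(chi-square > 4)) or 11.2% (3 df, P(chi-square > 6)). If the interaction is tested first and a kept interaction holds the main effect in, retention is about 1 − 0.843 × 0.843 = 29% with a 1-df interaction, or 1 − 0.843 × 0.865 = 27% with a 2-df one, treating the steps as independent.

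**The case against.** Several stronger readings are tempting, and the documents do not support them.

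- *The test of objective 4 loses its error rate.* It does not through this selection. Any term with p < 0.05 also passes p < 0.157, so the overall false-positive rate stays at 5%. The 32% is conditional on the term being kept and should not be set against 5%.
- *The cost ratio is biased away from 1.* With no true effect, kept estimates fall on both sides equally, so there is no signed bias, only inflated absolute size. There is upward bias for small true effects, but it is slight at the planned effect.
- *If the term is dropped there is no estimate at all.* Section 3.4.4 still gives the unadjusted association. Only the adjusted estimate is lost.
- *The planned confidence intervals are invalid.* Section 3.4.4 specifies none; the bootstrap intervals for cost ratios belong to sub-study 3. The coverage figures apply to any ordinary model-based interval taken from the selected model.
- *The adjusted estimate is missing in 84% of null cases.* That holds for a lone 1-df term. With the interaction as a candidate, the figure depends on how selection is run.

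It can also be said that the sentence promising relative costs for both groups implies that the term is meant to stay. That is probably the intent, but the stated rule does not secure it. Nor is this detail left to an unseen SAP: the selection rule is stated in the protocol, in the synopsis and again in section 3.4.4.

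**Conclusion.** The point holds in this limited form. A pre-named exposure, with its own hypothesis and sample size, is subject to deletion by AIC, and the adjusted relative cost comes from whatever model remains. What suffers is the adjusted estimate and any ordinary interval or p-value attached to it. The harm is greatest at null and small effects (kept 16% to 50% of the time for true effects of 0 to 0.1 SD, with 68% coverage when kept at the null). It is small at the planned 0.2 SD (about 8% dropped, +6%). These figures assume 2,200 patients, 10% prevalence, two-sided testing and a single 1-df exposure term.

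**What to change.** In section 3.4.4 and the synopsis, state that the high-eosinophil term (primary cut-point ≥ 0.45 × 10⁹/L) and the adjustment variables of section 3.3.2, including smoking status, are kept in both cost models, and that the adjusted cost ratio with its 95% CI is reported whatever its size. Align sections 2.5.4 and 3.3.3 with this.

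Report the eosinophil-by-smoking interaction from a separate pre-specified model, with a cost ratio for each smoking stratum, whether or not AIC favours it. It should not be forced into the main model, because there would then be no single cost ratio matching the 2,200 calculation. Say that power is lower: if one third are active smokers (the share section 3.6.1 expects in OPCRD, assumed here), 2,200 patients split into about 1,467 and 733, and power for 0.2 SD is about 63% in non-smokers and 37% in smokers.

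Confine AIC backward selection to the search for other cost drivers and label it exploratory.

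The cost is a few sentences. No new data are needed, and the 2,200 for the main contrast stands, since it already assumes a fixed two-group test.
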